# 7.7. Follow-up/censoring

The follow-up period will begin from 30 days after the index date (to allow development of immunity after vaccination) and will end at the earliest occurrence of the following events:

- HZ occurrence
- End of continuous enrolment (period of uninterrupted insurance coverage with gap allowance of 30 days).
- Death (date of death including the year and month of death).
- End of data availability/study period (December 31, 2021).
- Receipt of RZV (additional dose for vaccinated participants or first RZV dose in the case of unvaccinated participants):
  - For 2-dose VE, vaccinated participants will be censored upon receipt of a dose 3.
  - For 1-dose VE, vaccinated participants will be censored upon receipt of dose 2.
- Receipt of ZVL vaccination.

The latest date a patient can be enrolled to ensure minimum duration of follow up is 30 September 2021 to allow for at least 3 months follow-up to observe HZ.

### 8. STUDY PROCEDURES

Not applicable.

## 9. SAFETY

Not applicable.

### 10. DISCONTINUATION/WITHDRAWAL CRITERIA

Not applicable.

## 11. STATISTICAL CONSIDERATIONS

## 11.1. Sample size determination

Descriptive queries in the Optum™ database were performed to identify, obtain, and aggregate the number of ≥50 YOA US patients with AID using the algorithm definition presented in Section 7.5. The outputs of these queries will be used to define the AID populations in the study and inform the study design and SAP by refining the study methodology and analytical approaches most appropriate for the expected sample size. The outputs of these queries will be used to estimate:

The incidence rate of HZ in the unvaccinated group (Table 2).

• The sample size and average follow-up duration of vaccinated group (Table 3).

Table 2 Incidence rate of HZ in unvaccinated group by AID, Optum™ database 01/2018-12/2021\*

AID	Number of participants with HZ in unvaccinated group	Number of participants in unvaccinated group	Person-years (PY)	Incidence rate (1000 PY)
IBD	693	24234	51090	13.56
RA	2781	81639	179079	15.53
SLE	565	15644	33195	17.02
PsO	1533	60533	134443	11.40
PsA	499	14942	34023	14.67
MS	677	20407	48656	13.91

HZ= herpes zoster; SLE: systemic lupus erythematosus; MS: multiple sclerosis; RA: rheumatoid arthritis; IBD: inflammatory bowel disease; PsO: psoriasis; PsA: psoriatic arthritis.

Table 3 Sample size and average follow up time among 2-dose recipients, Optum database 01/2018-12/2021\*

Year of receipt of dose 2 RZV	Category	SLE	IBD	RA	Ps0	PsA	MS
	Average FU (years)	2.7	2.5	2.6	2.6	2.5	2.7
2018	N	269	640	1761	1280	277	299
	Average FU (years)	1.9	1.9	2.0	2.0	2.0	1.9
2019	N	831	1700	4787	3372	772	877
	Average FU (years)	1.2	1.3	1.2	1.2	1.2	1.2
2020	N	935	1906	5113	3996	967	997
	Average FU (years)	0.5	0.5	0.5	0.5	0.5	0.5
2021	N	875	1619	4267	3468	839	948
0	Average FU (years)	1.3	1.4	1.4	1.4	1.3	1.4
Overall	N	2910	5865	15928	12086	2845	3121

Average follow-up time (weighted): 1.4 year

RZV= recombinant zoster vaccine, FU = follow-up, N: number of participants with 2 doses RZV.

\* This represents the actual study population.

\* This represents the actual study population.

219111 (EPI-ZOSTER-097 VE US DB)
Protocol Final

A two-sided log rank test with an alpha of 5% is used for the sample size calculation of the primary VE objectives. Assumptions for sample size calculation are:

- Incidence of HZ in the RZV unvaccinated group: 12, 15, 20 /1,000 person-years [Baumrin, 2019; Izurieta, 2021; Kawai, 2017b], in accordance with the preliminary analysis performed in OptumTM database (Table 2)
- Detectable HR (or VE): 0.3, 0.4, 0.5 or 0.6 (VE=70%, 60%, 50%, or 40%)
- Ratio of RZV unvaccinated to RZV vaccinated group: 3:1
- Average follow-up period: 1 or 2 years after the second dose of RZV; the estimated average follow-up time in Optum database was 1.4 year (Table 3)
- Censoring rate in the RZV vaccinated group: 20%
- Censoring rate in the RZV unvaccinated group: 15%

Results of the sample size calculation are presented in Table 4:

Table 4 Sample size calculation\* for effectiveness analyses under a range of assumed incidence rates for unvaccinated group and different detectable VE

			Sample Size of RZV vaccinated group						
Power	Follow up time	Incidence rate in RZV unvaccinated group (/1000 person- years)	VE (70%)	VE (60%)	VE (50%)	VE (40%)			
		12	1398	2197	3545	6089			
	1 year	15	1120	1760	2840	4877			
90%		20	841	1323	2134	3666			
30 70	2 years	12	765	1203	1941	3333			
		15	614	965	1557	2673			
		20	462	726	1172	2013			
		12	1017	1599	2588	4463			
	1 year	15	815	1281	2073	3575			
80%		20	612	963	1558	2687			
OU 7/0		12	558	876	1418	2444			
	2 years	15	447	703	1137	1961			
		20	337	529	856	1477			

RZV= recombinant zoster vaccine, VE= vaccine effectiveness, % = Percentage. Sample size has been calculated for each of the six cohorts.

The number of potential participants who received 2 doses of RZV during the accrual period between 1/2018 to 12/2021 is 5865 for IBD, 2910 for SLE, 15928 for RA, 3121 for MS, 12086 for PsO, 2845 for PsA, respectively (Table 3). This exceeds the required numbers for a power of 80% and detectable VE of 50% (Table 4). This demonstrates that the study is sufficiently powered to assess the primary VE objectives. The sample size calculation is only for primary objectives.

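### Table 4 was computed with the 3:1 ratio inverted, so its sizes for 80% power give about 72–73% power at VE 50% under the stated design

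*Protocol*

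**What the plan says.** Protocol section 11.1 fixes the method: "A two-sided log rank test with an alpha of 5% is used for the sample size calculation of the primary VE objectives". Its assumptions are:

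- "Incidence of HZ in the RZV unvaccinated group: 12, 15, 20 /1,000 person-years"
- "Detectable HR (or VE): 0.3, 0.4, 0.5 or 0.6 (VE=70%, 60%, 50%, or 40" (per cent)
- "Ratio of RZV unvaccinated to RZV vaccinated group: 3:1"
- "Average follow-up period: 1 or 2 years after the second dose of RZV"
- "Censoring rate in the RZV vaccinated group: 20" (per cent)
- "Censoring rate in the RZV unvaccinated group: 15" (per cent)

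Table 4 then lists 48 sizes, all labelled as the vaccinated group. Sections 1.3, 5.1 and 7.6 also give 1 vaccinated to 3 unvaccinated, so the ratio is the design and not a slip in one line. After listing the available 2-dose recipients per disease, section 11.1 says: "This exceeds the required numbers for a power of 80% and detectable VE of 50% (Table 4"), and concludes that the study is sufficiently powered for the primary objectives.

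**The concern.** With a protective vaccine and 1 vaccinated to 3 unvaccinated, the small group is also the group with few events. That costs information compared with the reverse allocation, so the direction of the ratio matters for a log-rank size.

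Table 4 carries a sign of the wrong direction. Its 90% to 80% size ratio at VE 50% (12 per 1,000, 1 year) is 3545/2588 = 1.370. With equal null and alternative variances the ratio would be (3.2415/2.8016)² = 1.339. A larger ratio means that the alternative variance exceeds the null variance, which happens here only if the smaller group has the higher HZ rate. The design has the opposite.

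Table 4 is the only quantitative support for six primary objectives. If it belongs to another design, its power labels and the sentence drawn from it need correction.

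**Working it through.** **Inputs (section 11.1).** Two-sided alpha 0.05; unvaccinated rate 12, 15 or 20 per 1,000 person-years; HR 0.3 to 0.6; follow-up 1 or 2 years; censoring 20% (vaccinated) and 15% (unvaccinated). Censoring is read as yearly, with hazards −ln 0.80 and −ln 0.85. This reading is an assumption; it is the one that reproduces the table.

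**Formula.** Log-rank with separate null and alternative variances and exponential event and censoring times:

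N = (1.960·√V0 + z_power·√V1)² / drift²

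Here V0 = Σ D·φ(1−φ), V1 = Σ D·q(1−q) and drift = |Σ D·(q−φ)|. D is the expected number of events in a small time step, φ the small group's share at risk and q its share of events. All are per participant in the small group, and the large group is three times as big.

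**Step 1: reproduce the printed figure (12 per 1,000, 1 year, VE 50%, 80% power).** Inverted allocation: small group unvaccinated (rate 0.012, 15% censoring), large group vaccinated (rate 0.006, 20% censoring).

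- drift = 0.0041016, V0 = 0.0051475, V1 = 0.0065364
- N = [(1.960 × 0.07175 + 0.8416 × 0.08085) / 0.0041016]² = 2588; printed 2588

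Over all 48 cells the largest discrepancy is about 0.2%.

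**Step 2: same formula, stated orientation.** Small group vaccinated (0.006, 20%), large group unvaccinated (0.012, 15%).

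- drift = 0.0040478, V0 = 0.0071035, V1 = 0.0046132
- N = [(1.960 × 0.08428 + 0.8416 × 0.06792) / 0.0040478]² = 3017
- Power at 2588: Φ[(√2588 × 0.0040478 − 1.960 × 0.08428) / 0.06792] = Φ(0.600) = 72.6%

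Expected events at 2588 are 13.9 vaccinated and 85.5 unvaccinated in the stated design, against 41.6 vaccinated and 28.5 unvaccinated in the inverted one.

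**Step 3: all VE 50% rows for 80% power.**

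| Follow-up | Rate per 1,000 | Printed N | N, stated orientation | Power at printed N |
|---|---|---|---|---|
| 1 year | 12 | 2588 | 3017 | 72.6% |
| 1 year | 15 | 2073 | 2416 | 72.6% |
| 1 year | 20 | 1558 | 1815 | 72.6% |
| 2 years | 12 | 1418 | 1673 | 71.9% |
| 2 years | 15 | 1137 | 1341 | 72.0% |
| 2 years | 20 | 856 | 1008 | 72.0% |

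Over the whole table the stated orientation needs 7% to 31% more than printed. The sizes listed for 80% give 64–65% at VE 70%, 69–70% at VE 60% and 74–75% at VE 40%. Those listed for 90% give 86–87% at VE 50%.

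**Step 4: simulation (8,000 log-rank tests per setting; 12 per 1,000, 1 year, VE 50%).** 2588 vaccinated to 7764 unvaccinated: 72.1%. The same sizes inverted: 79.4%. 3018 to 9054 in the stated orientation: 79.8%. A separate run of 4,000 at 2588 to 7764 gave 74%.

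**Step 5: the cohorts (VE 50%, stated orientation).** Cohort sizes and follow-up are from Table 3, own rates from Table 2.

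| Cohort | N | 12 per 1,000, 1 year | Own rate, 1 year | Own rate, own average follow-up |
|---|---|---|---|---|
| SLE | 2910 | 78% | 92% (17.02) | 97% (1.3 years) |
| PsA | 2845 | 77% | 86% (14.67) | 93% (1.3 years) |
| MS | 3121 | 82% | 88% (13.91) | 96% (1.4 years) |

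IBD (5865) has 98% at 12 per 1,000 and 1 year. RA and PsO are far larger and are not in question.

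**The case against.** **The practical effect is small.** This stands. Cohort sizes come from the database and Table 4 drives no recruitment. The objectives are to estimate VE, and no estimate changes. The sentence fails for two of six cohorts in one row, and neither cohort has those parameters: SLE is at 17.02 and PsA at 14.67 per 1,000 person-years, each with 1.3 years of follow-up. Even at 12 per 1,000, 1.3 years gives about 88% and 87%. A reader might infer that the study is underpowered; the protocol's own Tables 2 and 3 do not support that.

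**A common formula would pass the printed size.** Schoenfeld in the stated orientation gives 2269 for the first cell, below 2588. But it does not reproduce the table, it ignores the direction of the imbalance, and at HR 0.5 with this allocation the simulations show it to be optimistic. Schoenfeld, Freedman and one-variance versions were tried in the stated orientation with several readings of the censoring. None returned the printed figures.

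**What exactly was swapped?** A reader might infer that the HZ rates were put on the wrong groups while the censoring stayed with group size (20% on the small group, 15% on the large). The fit does not support this: that set-up overshoots every cell by 0.9% to 2.7% (2618 against 2588; 1450 against 1418). Keeping rate and censoring with their proper groups and inverting only the ratio fits within about 0.2%.

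**Conclusion.** The point holds as an error in the stated figures. Table 4 belongs to a design with 3 vaccinated per 1 unvaccinated, and the column labelled as the vaccinated group is the unvaccinated group of that reverse design. For the design in the protocol, the printed sizes are too small in every cell, and the sizes listed for 80% power give about 72–73% at VE 50%. The comparison with the cohorts is true against the printed table, but in the corrected 12 per 1,000, 1-year row it fails for SLE and PsA by 2 to 3 percentage points of power.

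The inversion is inferred from the 48-cell match; the protocol does not show its calculation. The figures assume exponential event times, yearly censoring and distinct comparators. If the censoring percentages are entered directly as hazards (0.20 and 0.15), power at the printed VE 50% sizes is 72.9–73.1%, so the conclusion does not depend on that choice. Overall power for the planned cohorts remains adequate. Severity is moderate.

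**What to change.** Recompute Table 4 with 3 unvaccinated per 1 vaccinated, keeping the unvaccinated rate and 15% censoring on the larger group, and name the formula and the reading of the censoring rates. Replace the sentence that all cohorts exceed the required numbers with power per cohort at its Table 2 rate and Table 3 follow-up (for VE 50%, about 97% SLE, 93% PsA and 96% MS, with the larger cohorts higher). Note that SLE and PsA fall just short of 80% at 12 per 1,000 and 1 year.

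The cost is one rerun and one revised sentence. Design, cohorts and analysis do not change.

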# 11.2. Sets for analyses

Not applicable.

# 11.3. Statistical analysis

## 11.3.1. Sequence of analyses

All analyses, including descriptive, will be conducted separately for RA, IBD, SLE, MS, PsO, and PsA populations based on when information related to the medication categories for each AID becomes available. The analyses of RA and IBD will be performed first, followed by the analyses of SLE and MS and the analyses of PsO and PsA.

# 11.3.2. Primary analyses

For the primary objectives 1-6, the number of incident HZ cases and the number of person-years of follow-up for participants will be assessed for the 2-dose ( $\geq$  28 days apart) RZV cohort and the matched unvaccinated cohort. Crude VE (%) will be estimated as (1 – [incidence rate of HZ among 2-dose (at least 28 days apart) RZV recipients / incidence rate of HZ among RZV unvaccinated participants]) x 100%.

Adjusted HRs and 95% confidence intervals (CIs) comparing HZ incidence rates in the 2-dose ( $\geq$ 28 days apart) RZV cohort, and the matched unvaccinated cohort will be estimated by Cox proportional hazards regression models. Estimates of VE (%) will be calculated as (1 – adjusted HR) × 100%.

#### 11.3.3. Descriptive analyses

The number and characteristics of participants in each cohort will be described and compared. Categorical variables such as gender will be presented as absolute numbers and percentages with p-values for the Pearson  $\chi^2$  test or Fisher's exact test, as appropriate. Continuous variables such as age in years will be presented as the mean with standard deviation and/or median with interquartile ranges, with p-values for the two-sample t-test or Wilcoxon rank-sum test, as appropriate. Absolute standardized differences will be calculated to assess the balance of covariates with a cut-off value of 0.20. Overall incidence rates of HZ for the 2-dose ( $\geq$ 28 days apart) and the 1-dose RZV vaccinated cohort and the matched unvaccinated cohort will be calculated by dividing the number of HZ cases by the total number of person-years.

#### 11.3.4. Secondary analysis

**Secondary objective 1:** Analyses for secondary objective 1 will employ similar methods as for the primary analyses. Analyses for IBD (secondary objective 1) will be stratified by UC and CD. A separate VE for UC and CD will be estimated. Descriptive analyses and Cox proportional hazards regression will be conducted and estimates of VE (%) will be calculated as  $(1 - \text{adjusted HR}) \times 100$ .

219111 (EPI-ZOSTER-097 VE US DB) Protocol Final

**Secondary objective 2:** Analyses for secondary objective 2 will employ similar methods as for the primary analyses. Analyses for either PsO or PsA (secondary objective 2) will be performed. Descriptive analyses and Cox proportional hazards regression will be conducted and estimates of VE (%) will be calculated as  $(1 - \text{adjusted HR}) \times 100$ .

**Secondary objectives 3-9**: Analyses for secondary objectives 3-9 will employ similar methods as for the primary analyses and will be conducted among the matched 2-dose cohorts of participants with SLE (secondary objective 3), MS (secondary objective 4), RA (secondary objective 5), IBD (secondary objective 6), PsO (secondary objective 7), PsA (secondary objective 8), either PsO or PsA (secondary objective 9) who receive 2 doses of RZV ≥28 days apart. Analyses will be stratified by age group, gender, time since vaccination, time interval between two doses (≥28 days apart), and medication category (as described in Appendix 6) during baseline. Analyses for IBD (secondary objective 6) will be stratified by UC and CD. Two categories will be considered to differentiate UC and CD: UC, and CD. Analyses for either PsO or PsA (secondary objective 9) will be performed. Descriptive analyses and Cox proportional hazards regression will be conducted and estimates of VE (%) will be calculated as (1 – adjusted HR) × 100.

**Secondary objectives 10-16:** Analyses for secondary objectives 10-16 will employ similar methods as for the primary analyses and will be conducted among the matched 1-dose cohorts of participants with SLE (secondary objective 10), MS (secondary objective 11), RA (secondary objective 12), IBD (secondary objective 13), PsO (secondary objective 14), PsA (secondary objective 15), and either PsO or PsA (secondary objective 16). Analyses for either PsO or PsA (secondary objective 16) will be performed. Descriptive analyses and Cox proportional hazards regression will be conducted and estimates of VE (%) will be calculated as (1 – adjusted HR) × 100.

**Secondary objective 17:** Analyses for secondary objective 17 will employ similar methods as for the primary analyses and will be conducted among the matched 2-dose cohorts. Descriptive analyses and Cox proportional hazards regression will be conducted and overall estimates of VE (%) will be calculated for all selected AIDs as  $(1 - \text{adjusted HR}) \times 100$ .

## 11.3.5. Sensitivity analyses

Sensitivity analyses will be performed to assess if the occurrence of the COVID-19 pandemic has an impact on the effectiveness of the vaccine in participants who test positive for COVID-19 during the follow-up period. Methods to identify the COVID test result (i.e., PCR) and analyses to assess the impact of the pandemic on the VE will be described in the SAP. Sensitivity analyses will also be performed on participants who have either PsO or PSA, participants who have PsO only, participants who have PsA only, and participants who have both PsO and PsA to address the potential overlap between PsO and PsA. Further details of the sensitivity analyses will be described in the SAP.

219111 (EPI-ZOSTER-097 VE US DB) Protocol Final

## 11.3.6. Missing data

Missing data will be handled differently depending on the data. For demographic variables, the rate of missing data is <5% and so it's negligible. For healthcare cost level, a cost of zero will be considered if a vaccinated participant does not have any cost reported in the baseline period (such participants will be matched with unvaccinated participants with no cost reported, so missing data would not impact the analysis). For the other variables, these are based on ICD codes and the variables will be defined as Y/N format. Handling missing data using more complex methods is being reviewed. More details of the approaches to address missing data will be included in the SAP.

# 11.4. Data management

# 11.4.1. Data handling conventions

The Real-World Analytics (RWA) Team at GSK will coordinate all data management aspects for the proposed study. RWA in collaboration with the biostatistician will be responsible for writing and distributing SAS programs to use for evaluating data from the administrative claims Optum™ database. RWA will maintain a secure distributed querying web-based portal to enable secure distribution of analytic queries, data transfer, and document storage. The system will meet all required State and Federal security guidelines for health data (e.g., Federal Information Security Management Act [FISMA], Health Insurance Portability and Accountability Act of 1996), specifically FISMA compliant for FISMA security controls as specified in the National Institute of Standards and Technology (NIST) Special Publication 800-53 (NIST and Joint Task Force Transformation Initiative 2017).

219111 (EPI-ZOSTER-097 VE US DB) Protocol Final

### 13. APPENDICES

## 13.1 Appendix 1: Abbreviations and glossary of terms

### 13.1.1. List of abbreviations

**ACIP** Advisory Committee on Immunization Practices

**AE** Adverse Event

**AID** Autoimmune Disease

**AuHSCT** Autologous Hematopoietic Stem Cell Transplants

**CD** Crohn's Disease

**CDM** Clinformatics Data Mart

**CPT** Current Procedural Terminology

**E H R** Electronic Health Record

**ED** Emergency Department

**FDA** Food and Drug Administration, United States of

America

**GSK** GlaxoSmithKline

**HM** Hematological Malignancies

**HZ** Herpes Zoster

**IBD** Inflammatory Bowel Disease

IC Immunocompromised

ICD International Classification of Diseases

**IDNs** Integrated Delivery Networks

MS Multiple Sclerosis

**NDC** National Drug Code

**PHN** Post Herpetic Neuralgia

**PPV** Positive Predictive Value

219111 (EPI-ZOSTER-097 VE US DB) Protocol Final

**PsA** Psoriatic Arthritis

**PsO** Psoriasis

**RA** Rheumatoid Arthritis

**RCT** Randomized Controlled Trial

**RWA** Real World Analytics

**RZV** Recombinant Zoster Vaccine

**SLE** Systemic Lupus Erythematosus

UC Ulcerative Colitis

**VE** Vaccine effectiveness

VZV Varicella Zoster Virus

YOA Years of Age

**ZVL** Zoster vaccine Live

## 13.1.2. Glossary of terms

Eligible: Qualified for enrollment into the study based upon strict

adherence to inclusion/exclusion criteria.

**Essential documents:** Documents which individually and collectively permit

evaluation of the conduct of a study and the quality of

the data produced.

eTrack: GSK's tracking tool for clinical trials.

**Investigator:** A person responsible for the conduct of the clinical trial

at a trial site. If a trial is conducted by a team of individuals at a trial site, the investigator is the responsible leader of the team and may be called the

principal investigator.

The investigator can delegate trial-related duties and functions conducted at the trial site to qualified

individual or party to perform those trial-related duties

and functions.

219111 (EPI-ZOSTER-097 VE US DB)
Protocol Final

**Participant:** Term used throughout the protocol to denote an

individual who has been contacted to participate or who participates in the clinical study as a recipient of the study intervention (vaccine(s)/product(s)/control).

**Study intervention:** Any investigational or marketed product(s) or placebo

intended to be administered to a participant during the

study.

### 13.2. Appendix 2: Study governance considerations

## 13.2.1. Regulatory and ethical considerations

- This study will be conducted in accordance with the protocol and:
  - Ethical principles derived from international guidelines including the Declaration of Helsinki and Council for International Organisations of Medical Sciences (CIOMS) International Ethical Guidelines
  - Food and Drug Administration (FDA) Code of Federal Regulations Title 21 (21 CFR)
  - All other applicable regulations and local laws

## 13.2.2. Data protection

Data privacy is protected by using anonymized data.

### 13.2.3. Dissemination of study data

- The key design elements of this protocol and results summaries will be posted on GSK Clinical Study register in compliance with the applicable regulations/GSK policy according to the timelines described below
- Protocol summaries will be registered prior to study start.
- Results summaries will be posted within 12 months of analysis completion date.
- Where required by regulation, summaries will also be posted on applicable national or regional clinical trial registers.

